
Section 3.7, Trial Procedures, Table 3.7-1
	
Footnote a: ^aThe last visit assessments from the previous protocol can be combined with the screening visit for this trial, with all required assessments from each visit performed only once. ... Footnote g: ^gA full liver function panel (AST, ALT, alkaline phosphatase, BT) will be done at screening. All other liver function tests at subsequent visits are for ALT only, unless otherwise clinically indicated. Any transaminase values which exceed 2 × ULN should prompt immediate retesting within 72 hours. While values remain in an abnormal range, testing frequency should be increased to at least weekly for the first month, gradually returning to monthly, and every 3 months as indicated by the results. Local liver function panel analyses will also be performed more frequently, if necessary. ... Footnote l: ^lIf during the titration contact the determination is made to adjust the dose regimen, dose adjustments will be made using dispensed supply, and dose instructions will be provided by the investigator. The subject’s current dose will be entered into the interactive response technology (IRT) at each visit. Drug dispensation/reconciliation will be conducted on a monthly basis for subjects who have monthly trial visits and once every 3 months for subjects who have trial visits every 3 months. ...
	
Footnote a: ^aThe last visit assessments from the previous trial can be combined with the screening and baseline visits for this trial, with all required assessments from each visit performed only once. ... Footnote g: ^gA full liver function panel (AST, ALT, alkaline phosphatase, BT) will be done at screening. All other liver function tests at subsequent visits are for ALT only, unless otherwise clinically indicated. An ALT elevation > 2 × ULN should trigger prompt testing of hepatic function within 72 hours. Any transaminase values which exceed 2 × ULN should prompt immediate retesting within 72 hours. While values remain in an abnormal range, testing frequency should be increased to at least weekly for the first month, gradually returning to monthly, and every 3 months as indicated by the results. Local liver function panel analyses will also be performed more frequently, if necessary. ... Footnote l: ^lIf during the titration contact the determination is made to adjust the dose regimen, dose adjustments will be made using dispensed supply, and dose instructions will be provided by the investigator. The subject’s current dose will be entered into the interactive response technology (IRT) at each visit. Drug dispensation/reconciliation will be conducted on a monthly basis for subjects who have monthly trial visits and once every 3 months for subjects who have trial visits every 3 months. If additional drug supply is required for titration purposes, the site will arrange a subject visit for


Protocol 156-13-211

[figure not shown]
Location	Old Text	Updated Text
		dispensation. ...
Section 3.7.1.1, Screening (-30 days to 1 day prior to Baseline)	Screening for eligibility is required for all subjects. The screening visit may be combined with the last visit from the previous protocol with all required assessments from each visit only performed once. In some cases, if a subject enrolls in this trial from a prior tolvaptan trial, the end of trial visit for that trial and the screening visit for this one may occur simultaneously. Required assessments are as follows: 1. Obtain subject consent. 2. Determine subject eligibility through inclusion/exclusion criteria. 3. Record demographic information and prior trial identifiers (screening identification [ID], subject ID, site ID, prior tolvaptan ADPKD trial protocol number). 4. Record medical/ADPKD history using prior trial data. 5. Review dietary recommendations and compliance ...	Screening for eligibility is required for all subjects. The screening and baseline visits may be combined with the last visit from either the 156-08-271 or 156-13-210 protocol with all required assessments from each visit performed only once. Therefore , in some cases, if a subject enrolls in this trial from a prior tolvaptan trial, the end of trial or last follow-up visit for that trial and the screening and baseline visit for this one may occur simultaneously. Required assessments for the screening visit are as follows: 1. Obtain subject consent. 2. Obtain subject's new screening identification (ID) assigned by interactive response technology (IRT). 3. Determine subject eligibility through inclusion/exclusion criteria. 4. Record demographic information and prior trial identifiers (screening ID, subject ID, prior tolvaptan ADPKD trial protocol number). 5. Record medical/ADPKD history using prior trial data. 6. Review dietary recommendations and compliance ...
Section 3.7.2.4.1 Liver Test Abnormalities and Interruption/Discontinuation of Investigational Medical Product	The appearance of any suspicious symptom or sign should trigger prompt testing of hepatic function (ie, within 72 hours). Local laboratory testing is acceptable, ideally with a concurrent central laboratory sample for confirmation.	An ALT elevation $> 2 \times$ ULN or the appearance of any suspicious symptom or sign should trigger prompt testing of hepatic function (ie, within 72 hours). Local laboratory testing is acceptable, ideally with a concurrent central laboratory sample for confirmation.
Section 3.7.5, Treatment Interruption and Discontinuation	... A subject who permanently discontinues IMP treatment may have the option to end trial participation (complete the early termination visit)	... A subject who permanently discontinues IMP treatment ends trial participation and the early termination visit should be

Protocol 156-13-211

[figure not shown]
Location	Old Text	Updated Text
	or to continue participation off IMP and complete ongoing trial assessments as per protocol or with a modified (ie, less frequent) schedule as outlined in Section 3.8.3.	completed.
Section 5.2, Eliciting and Reporting Adverse Events	... In addition, the sponsor must be notified immediately by telephone or fax of any immediately reportable events according to the procedure outlined below in Section 5.3. In addition, Quintiles (drug safety service) must be notified immediately by telephone or fax of any immediately reportable events according to the procedure outlined below in Section 5.3. ...
Section 5.3, Immediately Reportable Events	The investigator must immediately report within 24 hours after either the investigator or site personnel become aware of any SAE, new liver laboratory abnormality requiring special liver eCRF completion, or confirmed pregnancy, by telephone or by fax to the sponsor as outlined in Appendix 1. ...	The investigator must immediately report within 24 hours after either the investigator or site personnel become aware of any SAE, new liver laboratory abnormality requiring special liver eCRF completion, or confirmed pregnancy, by telephone or by fax to Quintiles (drug safety service) as outlined in Appendix 1. ...

Protocol 156-13-211

List of Abbreviations and Definition of Terms

Abbreviation	Definition
AE	Adverse event
ALP	Alkaline phosphatase
ALT	Alanine aminotransferase
AST	Aspartate aminotransferase
BUN	Blood urea nitrogen
CRF	Case report form
CRO	Clinical Research Organization
ECG	Electrocardiogram
EDC	Electronic data capture
EU	European Union
EudraCT	European Clinical Trial Data Base
FDA	(United States) Food and Drug Administration
GCP	Good Clinical Practice
ICF	Informed consent form
ICH	International Conference on Harmonisation
IMP	Investigational medicinal product
IND	Investigative new drug
IRB	Institutional review board
IRE	Immediately reportable event
MedDRA	Medical Dictionary for Regulatory Activities
PE	Physical examination
SAE	Serious adverse event
TEAE	Treatment-emergent adverse event
US or USA	United States or United States of America
ULN	Upper limit of normal

Protocol 156-13-211

1 Introduction

This Statistical Analysis Plan (SAP) documents the statistical methodology and data analysis algorithms and conventions to be applied for statistical analysis and reporting of efficacy and safety data of study 156-13-211. The original protocol (dated 20 May 2014), the Amendment 1 (dated 14 July 2014), and the Amendment 2 (dated 06 March 2015) are taken into consideration in developing this SAP.

2 Trial Objective

The primary objective of this trial is to evaluate and describe the long-term safety of Tolvaptan.

3 Trial Design

3.1 Design of Trial

This trial is a phase 3b, multi-center, open-label trial. Eligible subjects have an opportunity to be enrolled into Trial 156-13-211 following completion of the follow-up visit(s) of the previous trial.

Eligible subjects from Trials 156-08-271 and 156-13-210 can have the last visit assessments from their previous respective protocols (end of trial visit for 156-08-271 subjects and last follow-up visit for 156-13-210 subjects) overlap the first visit in this trial. These last visit assessments can be combined with the screening and baseline visits for this trial, with all required assessments from each visit performed only once, so long as the time between the last visit assessments from the previous trial and the screening visit for this trial is within 30 days. If the first visit in this trial combines the last visit from a previous trial with both the screening and the baseline visits in this trial, the results from laboratory assessments performed at this combined visit will not be immediately available. Should any laboratory abnormalities be identified, the investigator will need to notify the subject and provide instructions regarding dosing or returning to the site for additional assessments.

Medical monitor approval is needed for enrollment of subjects whose completion of the preceding trial prior to entry in this trial exceeds 3 months, and these subjects will be required to undergo all screening and baseline assessments.

After consenting, subjects will be assigned a new screening number. Subjects who are found to be eligible will retain the same subject number they had been assigned in their

Protocol 156-13-211

previous trial. For purposes of ensuring subject safety, tolvaptan exposure of at least 18 months is required for all subjects.

While Trial 156-13-210 remains blinded, subjects enrolling from any prior trial besides Trial 156-08-271 are scheduled to have monthly hepatic monitoring for the first 18 months of this trial. After that, following the approval of the medical monitor, hepatic monitoring will take place every 3 months. Subjects enrolling from Trial 156-08-271 will have hepatic monitoring every 3 months. All Trial 156-13-210 subjects who are eligible for this trial will initially be scheduled to have trial visits and hepatic monitoring monthly for the first 18 months, then every 3 months thereafter, because their tolvaptan exposure cannot be determined since Trial 156-13-210 is a double blind trial. Once unblinding occurs, it can be determined which subjects received tolvaptan in Trial 156-13-210. These subjects may have their trial visits/hepatic transaminase monitoring changed to every 3 months sooner as their previous tolvaptan exposure in Trial 156-13-210 can count towards the 18-month threshold. Subjects from prior tolvaptan trials other than Trial 156-08-271 will have monthly trial visits/ALT level assessments for the first 18 months. After that, the trial visits/ALT monitoring will be conducted every 3 months after the change in frequency is confirmed with the medical monitor.

[figure not shown]
Enrollment in this trial will be closed when the last eligible subject from Trial 156-13-210 enrolls in this trial.

The duration of this trial is planned to continue

- Until the last subject from Trial 156-13-210 completes 18 months of tolvaptan treatment in this trial
- Subjects enrolling from other trials will conclude their participation once tolvaptan becomes available through routine prescription or through a compassionate use or named-patient program). Trial 156-13-210 subjects may opt to conclude their participation in this trial if tolvaptan becomes available before they complete 18 months of treatment in this trial

The study schema, presented in [Figure 3.1-1](#), depicts the overall study design.

Protocol 156-13-211

Figure 3.1-1 Study Design and Treatment Schema -Extension Study

Note: FU=follow-up

3.2 Treatments

The dose regimens to be used in this trial are 15/15 mg, 30/15 mg, 45/15 mg, 60/30 mg, and 90/30 mg.

Subjects will receive open-label tolvaptan for the duration of the trial. All subjects will be administered tolvaptan tablets in a daily split-dose, once upon awakening and another approximately 8 to 9 hours later (twice daily dosing). The exact time of dosing may be adjusted based on wake/sleep habits (eg, standard 8 AM and 5 PM may be switched to 10 PM and 7 AM if working a night shift). However, dosing times should be consistent for each individual's daily dose to maximize receptor suppression. Doses will be recorded as early dose/late dose (eg, 60/30 mg).

A subject's starting dose in this trial will be dependent on the trial in which they were previously enrolled:

- **156-13-210-** initiated on tolvaptan at a split-dose of 45/15 mg with upward titration every 3 to 4 days to 60/30 mg or 90/30 mg per day according to tolerability
- **156-08-271-** will retain the last dose level from 271 and start at the same dose in this trial

Protocol 156-13-211

- **Prior tolvaptan trials-** initiated on tolvaptan at a split-dose of 45/15 mg with upward titration every 3 to 4 days to 60/30 mg or 90/30 mg per day according to tolerability.

Down titration to 30/15 mg and 15/15 mg is also permitted at the discretion of the investigator according to subject tolerability with medical monitor notification. Further down titration to 30 or 15 mg once daily may be allowed only for metabolic drug-drug interaction and requires medical monitor approval.

3.3 Trial Population

This trial will include approximately 2,500 subjects over the age of 18 years with ADPKD diagnosed by Pei-Ravine criteria^{1,2} (modified by magnetic resonance imaging [MRI]) who completed or participated in a prior tolvaptan trial.

3.4 Trial Visit Window

Due to the extended duration of the study, the individual patient data will be summarized by period.

For assessments recorded at clinic visits, except for the hepatic monitoring for the subjects from Trial 156-08-271, data will be derived by mapping the study day of the assessment into corresponding time windows as specified in [Table 3.4.1](#). Study day is calculated as: date of assessment - date of enrollment (ie, screening or baseline date) + 1. If there are multiple observations within the same study time window, only the last observation within that study week will be used for the summary tables. The time window mapping rules are applicable to all post first dose safety and efficacy assessments (unless otherwise stated) that are assessed at the scheduled or unscheduled visits (excluding early termination visits/end of treatment visits).

Table 3.4.1 Mapping of clinic visit assessments to study month (except for hepatic monitoring for Subjects from Trial 156-08-271)

Study Month	Study Day Interval
Monthly Visit	
Month 1	2 – 46
Month 2	47 – 76
Month 3	77 – 107
Month 4	108 – 137
Month 5	138 – 168
Month 6	169 – 198
Month 7	199 – 229
Month 8	230 – 259
Month 9	260 – 290
Month 10	291 – 320
Month 11	321 – 351
Month 11	352 – 381
Month 13	382 – 412
Month 14	413 – 442

Protocol 156-13-211

Month 15	443 – 473
Month 16	474 – 503
Month 17	504 – 534
Month 18	535 – 595
Every 3 Months	
Month 21	596 – 686
Month 24	687 – 778
Month 27	779 – 869
Month 30	870 – 961
Month 33	962 – 1052
Month 36	1053 – 1144
Month 39	1145 – 1235
Month 42	1236 – 1327
Month 45	1328 – 1418
Month 48	1419 – 1510
Month 51	1511 – 1601
...	...

Note: Early Termination/End of Treatment (\pm 7 days)

Once Trial 156-13-210 unblinding occurs, it can be determined which subjects received tolvaptan in Trial 156-13-210. These subjects may have their trial visits/hepatic transaminase monitoring changed to every 3 months sooner as their previous tolvaptan exposure in Trial 156-13-210 can count towards the 18-month threshold.

For assessments for hepatic monitoring recorded at clinic visits, for the subjects from Trial 156-08-271, data will be derived by mapping the study day of the assessment into corresponding time windows as specified in [Table 3.4.2](#).

Study Month	Study Day Interval
Every 3 Months (\pm 45 days)	
Month 3	2 – 137
Month 6	138 – 229
Month 9	230 – 320
Month 12	321 – 412
Month 15	413 – 503
Month 18	504 – 595
Month 21	596 – 686
Month 24	687 – 778
Month 27	779 – 869
Month 30	870 – 961
...	...

Note: Early Termination/End of Treatment (\pm 7 days)

4 Sample Size

Sample size was not determined by a formal computation to achieve a target power. No efficacy analyses are planned. It is expected that approximately 2,500 subjects may enroll from previous tolvaptan trials.

Protocol 156-13-211

5 Statistical Analysis Datasets

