2.1 Trial Rationale

Evidence from previous studies suggests that during the first 18 months of long-term treatment in subjects with ADPKD, ALT and/or aspartate aminotransferase (AST) elevations and evidence of idiosyncratic DILI occurs at a greater frequency in tolvaptan treated subjects. However, the rate of new transaminase elevations beyond 18 months and up to 4.5 years was similar between tolvaptan treatment and placebo subjects.

Over the 3 years of placebo-controlled treatment, ALT was elevated to a greater than three times the upper limit of normal ($> 3 \times \text{ULN}$) in 4.4% of tolvaptan subjects compared with 1% of placebo subjects. To date, 3 tolvaptan subjects' transaminases and bilirubin levels reached Hy's laboratory criteria ($> 3 \times$ and $> 2 \times \text{ULN}$, respectively). Upon discontinuation, all subjects' liver tests showed reversibility of the elevation within approximately 4 months after tolvaptan was discontinued. Nevertheless, without adequate monitoring and management, it is estimated that a 1:4,000 risk for irreversible liver injury may exist.

Through more frequent (eg, monthly) monitoring of liver transaminases, the current trial will more precisely define the potential for DILI previously observed in Trial 156-04-251. Frequent monitoring will also detect smaller elevations earlier permitting closer and more thorough evaluation and intervention (including drug interruption or discontinuation). This is expected to mitigate the risk of serious or irreversible injury.

CCI [Redacted text block]

Protocol 156-13-211

CCI

This trial will extend our understanding of tolvaptan's long-term safety in ADPKD patients.

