8.3 Vital Signs Data

Summary statistics for changes from baseline in vital signs and potentially clinically significant results in vital signs will be summarized by parent study (and prior treatment).

Incidence of potentially clinically significant vital sign results will be summarized by parent study (and prior treatment). Criteria of potentially clinically significant vital sign abnormalities are provided in [Appendix 2](#).

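### The SAP clock starts at Trial 211 enrolment and no hepatic output is split by cumulative tolvaptan exposure, so exposure below and above 18 months stays mixed in some groups

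*SAP*

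**What the plan says.** Trials 156-13-210, 156-08-271 and 156-13-211 are called 210, 271 and 211 below.

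**The clock.** SAP 3.4 opens with "Due to the extended duration of the study, the individual patient data will be summarized by period" and then defines the time scale: "Study day is calculated as: date of assessment - date of enrollment (ie, screening or baseline date) + 1". Its scope is broad: "The time window mapping rules are applicable to all post first dose safety and efficacy assessments (unless otherwise stated"). Hepatic monitoring in 271 subjects has its own table of 3-month windows, but on the same scale: "for the subjects from Trial 156-08-271, data will be derived by mapping the study day of the assessment into corresponding time windows". SAP 3.4 also notes that tolvaptan taken in 210 counts toward the 18-month threshold, but it uses this only to explain a change of visit frequency.

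**The hepatic question.** Protocol 2.1 frames the risk by time on drug: "Evidence from previous studies suggests that during the first 18 months of long-term treatment in subjects with ADPKD", transaminase elevations and drug-induced liver injury (DILI) were more frequent on tolvaptan. Later, "the rate of new transaminase elevations beyond 18 months and up to 4.5 years was similar between tolvaptan treatment and placebo subjects". The same section expects this trial to define the DILI potential more precisely. The Protocol Synopsis ties monthly hepatic monitoring to accumulated exposure of 18 months.

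**The strata.** SAP 6.1 names three parent-study groups: 271, 210 and Other Trials. SAP 8.3 and 8.4 report vital signs and sodium "summarized by parent study (and prior treatment").

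**The hepatic outputs.** Protocol 3.5.1 and SAP 8 list frequency and time to onset of transaminase elevations. The readable part of the SAP laboratory section promises an incidence table and a listing for Hy's law criteria, with no split by exposure time.

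**The concern.** The safety question is posed in months of tolvaptan, while the tables count months since entering 211. For subjects who arrive with different amounts of prior drug, one trial month stands for different exposure. Trial Month 18 is exposure month 18 for a 210 placebo subject, up to about month 30 for a 210 tolvaptan subject, and month 36 or later for a 271 subject.

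What is at stake is how clearly the report can describe the contrast on which the protocol's rationale rests: a raised rate of liver signals up to 18 months of treatment and a background rate afterwards. In a group that crosses 18 months partway through the trial, a single figure averages the two periods. It understates the early rate and overstates the late one.

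**Working it through.** The plan has no figure of its own to reproduce. The 2,500 subjects are an expected enrolment, and SAP 8 excludes inferential analysis.

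**Inputs**
- ALT above 3 × ULN over 3 years: 4.4% tolvaptan, 1% placebo (Protocol 2.1).
- Later rate similar to placebo after 18 months (Protocol 2.1).
- Prior exposure of 271 subjects: at least 18 months (Protocol 1.3).
- Prior exposure of 210 tolvaptan subjects: at most about 12 months. The 12-month period includes post-treatment follow-up and may have been off treatment (Protocol 3.4.2), so 9 and 6 months are shown as well.

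**Step 1. Where each group crosses 18 months.** Trial months left in the early window = max(0, 18 − prior months).

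| Prior tolvaptan | Trial months before 18 | Share of trial Months 0-18 |
|---|---|---|
| 0 (210 placebo) | 18 | 100% |
| 6 | 12 | 67% |
| 9 | 9 | 50% |
| 12 | 6 | 33% |
| ≥18 (271) | 0 | 0% |

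With 12 months' prior exposure the crossing falls at 6 × 30.4375 ≈ day 183, inside the Month 6 window of SAP Table 3.4.1 (days 169-198). The first and last rows are unmixed, apart from an offset of up to 30 days for 210 placebo subjects if the screening date serves as enrolment. The middle rows are mixed.

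**Step 2. Illustrative early and late rates.** Assume that all excess falls in the first 18 months, that the hazard is constant within each period, and that percentages can be read as rate × time with full follow-up.
- Late rate = 1% / 3 y = 0.33 per 100 person-years (PY), or 0.5% per 18 months.
- Early rate = (4.4% − 0.5%) / 1.5 y = 2.6 per 100 PY.

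**Step 3. What trial Months 0-18 would show in 210 tolvaptan subjects.**
- 12 months prior: (0.5 × 2.6 + 1.0 × 0.333) / 1.5 = 1.09 per 100 PY.
- 9 months prior: (0.75 × 2.6 + 0.75 × 0.333) / 1.5 = 1.47 per 100 PY.
- 6 months prior: (1.0 × 2.6 + 0.5 × 0.333) / 1.5 = 1.84 per 100 PY.

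These are 42%, 56% and 71% of the early rate, and about 3.3, 4.4 and 5.5 times the late rate. The figure drops below half the early rate (1.3) only when (18 − p)/18 < (1.3 − 0.333)/(2.6 − 0.333) = 0.427, that is, when prior exposure p exceeds about 10.3 months.

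**Step 4. Pooled columns.** If f is the share of trial Months 0-18 spent below 18 months of exposure, the pooled 18-month risk is 0.5% + 3.4% × f: 1.2% at f = 0.2, 2.2% at f = 0.5 and 3.2% at f = 0.8. The documents give no enrolment mix by parent study, so f is unknown.

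**The case against.** The strongest reply is that the strata already do much of the work. Wherever results are split by parent study and prior treatment, 271 subjects are a late-exposure group and 210 placebo subjects an early-exposure group, so the early-late contrast is available without a new clock. This stands. It limits the point to 210 tolvaptan subjects, the Other Trials group (which admits subjects who interrupted or discontinued treatment, Protocol 3.4.2) and any pooled column.

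A reader might infer that the hepatic results are shown to be mistimed, for example that an elevation at trial Month 4 in a 210 tolvaptan subject will be reported as early onset. The documents do not support that. Time to onset is named without an origin in the readable text. The opening of SAP 8.2, where origin and strata might be set, is missing from the available text, and that gap is not a fault in the plan. The adverse event and Hy's law outputs are overall incidences, so the visit windows do not time them. What they lack is an exposure split.

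A reader might also infer that the trial cannot test whether risk falls after 18 months. That does not fit a trial which is descriptive by design and whose strata already give part of the contrast.

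Finally, the monitoring rule is not purely exposure-based: Table 3.7-1, footnote e, has subjects from other trials monitored monthly for their first 18 months in this trial. This is correct, but it does not touch the rationale in Protocol 2.1, which concerns time on treatment.

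**Conclusion.** The point holds in a limited form. The SAP's defined time scale is days since 211 enrolment, and no readable text reports hepatic results by cumulative exposure, although the protocol's liver rationale turns on 18 months of treatment. Exposure on either side of that threshold remains mixed in three places: 210 tolvaptan subjects, Other Trials, and pooled columns.

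For 210 tolvaptan subjects the illustration gives 1.09 to 1.84 per 100 PY against assumed rates of 2.6 early and 0.33 late. It rests on the assumptions in Step 2, and it gives subjects with prior exposure the same hazard as new starters. The latter is doubtful, because exclusion criterion 6 (Protocol 3.4.3) removes subjects with significant prior tolvaptan-related liver injury. The effect on the whole trial cannot be sized without the enrolment mix. This is an inexpensive improvement to the description of the main safety question, not a flaw that invalidates the planned tables.

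**What to change.** In SAP 3.4 and 8:

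- Define cumulative tolvaptan exposure as parent-trial plus 211 exposure, with a rule for gaps. Protocol 3.7.5 expects treatment interruptions, and Protocol 3.1 allows entry more than 3 months after the preceding trial with approval.
- State the time origin for time to onset of transaminase elevations.
- Add a table of ALT/AST elevations, Hy's law cases and liver adverse events per 100 PY by cumulative exposure, <18 versus ≥18 months. Let each subject contribute 211 person-time to both strata, with delayed entry at their prior exposure. A subject with 12 months' prior exposure adds 6 months of treatment to the first stratum and later time to the second.
- Note beside the table that entrants with prior exposure are selected for having tolerated it.
- Keep the existing trial-month and parent-study tables.

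The cost is merging parent-trial dosing data and producing a few extra tables. The sponsor already needs 210 exposure, after unblinding, to apply the 18-month rule. No visit or procedure changes.
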